significantly increased in those who responded to the 400 mg dose of droxidopa compared to the non-responders (105 ± 10 vs. 81 ± 10 mmHg, respectively; $p=0.0048$), and although the magnitude of effect was doubled in the non-responders, the SBP response did not differ significantly (9.0 ± 10 vs. 18.6 ± 16 mmHg, respectively; $p=0.2937$). These data suggest that individuals with a seated SBP below 95 mmHg may need a higher dose of droxidopa to normalize SBP.

d) Research Design and Methods

We propose to determine the dose of droxidopa that normalizes seated SBP in hypotensive individuals with SCI, and to determine the effect of that dose of droxidopa on supine BP, orthostatic BP and CBFv compared to placebo.

Study Population: Fifty subjects with SCI will be screened for study eligibility. We anticipate that approximately 40 of the subjects screened will be eligible and will undergo the dose optimization trial (**Study 1**). We anticipate that 25 subjects will respond to droxidopa with a normal seated SBP, and these individuals will be eligible for the randomized placebo-controlled trial to determine the effect of the optimal dose on supine BP, orthostatic BP and CBFv compared to placebo (**Study 2**). Each subject will be randomized by the Research Pharmacy to receive either droxidopa/placebo or placebo/droxidopa for the placebo-controlled prospective trial. Randomization will occur in a double-blinded manner. Study medication and placebo will be distributed by the James J Peters VAMC Pharmacy Service. The study is proposed to be completed in two years. Total enrollment will be accomplished within 18 months of obtaining full IRB approval, which should be complete within 6 months of funding, and subject participation is estimated to last about 6-8 weeks. A complete description of the study population can be found in the Human Subjects Form 11.

Study Procedures: Identical testing procedures will be performed at the JJP VAMC and the ISMMS according to the table below.

Procedures Table	Screening	Study 1									Study 2	
		1	2	3	4	5	6	7	8	9	10	11
Visit												
Medical Intake	X											
Medical History	X											
OH Survey	X											
AD Survey	X											
Seated BP	X	X	X	X	X	X	X	X	X	X	X	
Supine BP	X										X	X
HUT BP											X	X
CBFv											X	X
Side-effects		X	X	X	X	X	X	X	X	X	X	X
OH Symptoms Survey											X	X
Fatigue Survey	X										X	X

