Screening Visit – Individuals with SCI will be approached by investigators and asked to provide informed consent to participate in a screening study to determine eligibility. Compression garments will be removed, if tolerated, prior to assessment of supine and seated BP.

Any subject taking a vasoconstrictor agent will be asked to stop these medications 2 days or 5 half-lives (whichever is longer) prior to the screening visit, if medically cleared. The screening assessments will include: medical intake information (Appendix 1), medical history (Appendix 2), physical examination, American Spinal Cord Injury Impairment Scale (AIS) classification (if not assessed in the prior 6-months), clinical symptoms survey for OH and AD (Appendix 3) and

brachial BP assessment, recorded one time per minute for 10 minutes while in the seated and supine positions. Individuals will be eligible to participate in the study if 1) the average seated BP meets the WHO definition of hypotension (i.e., SBP \leq 110 mmHg for males or SBP \leq 100 mmHg for females) or 2) there is evidence of OH (i.e., orthostatic fall in BP \geq 20/10 mmHg when moved from the supine to the seated position) and 3) there is no evidence of sustained elevation in BP \geq 140/100 mmHg in either the supine or seated positions. This visit will take about 2 hours.

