This is a pilot trial to determine the dose efficacy and safety of droxidopa to increase systemic BP and improve orthostatic BP and CBFv responses compared to placebo in hypotensive individuals with SCI. Because this is a pilot trial, the following statistical analyses are not powered for a specific effect size; however, the results will be used to power a subsequent large scale clinical trial to identify the utility and safety of droxidopa for treatment of asymptomatic hypotension in persons with SCI.

Primary Aim 1.1: Dose optimization, open-label trial to determine the proportion of subjects with SCI with a normotensive response to droxidopa (**Efficacy #1**). Normotension will be defined as an average systolic BP (SBP) recorded 60-120 minutes after dose administration of between 111-139 mmHg in males and 101-139 mmHg in females.

- **Hypothesis 1.1** – Seated SBP will be normalized in 60% of the study sample following administration of droxidopa.
 - This hypothesis will be tested by constructing a 95% confidence interval about the sample proportion of cases in which BP is normalized with droxidopa. The inclusion of the 60% value in the confidence interval will be taken as evidence in support of the hypothesis. Further, the point estimate and confidence interval will provide the first reported estimate of the BP normalizing effect of droxidopa in the population with SCI.

Primary Aim 1.2: Dose optimization, open-label trial to determine the proportion of subjects with SCI with a hypertensive response to droxidopa (**Safety #1**). Hypertension will be defined as a sustained elevation in seated SBP \geq 140/100 mmHg or intolerable side effects considered related to study medication

- **Hypothesis 1.2** – Less than 10% of the study sample will exhibit hypertension or intolerable side effects related to administration of droxidopa.

- This hypothesis will be tested by constructing a 95% confidence interval about the proportion of cases in which either seated BP $\geq 140/100$ or intolerable side effects occur. If the 95% CI excludes values $\geq 10\%$, this will be taken as evidence in support of the hypothesis. Further, the point estimate and confidence interval will provide the first reported estimate of the expected side effects of droxidopa treatment in the population with SCI.

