Secondary Aims: To determine the effect of the individualized optimal dose of droxidopa, compared to placebo, on (1) supine BP (**Safety #2**), (2) SBP during a head-up tilt (HUT) maneuver to 70° (**Efficacy #2**) and change in cerebral blood flow velocity (CBFv) from supine to HUT (**Efficacy #3**). The following hypotheses will be tested in hypotensive individuals with SCI:

- **Hypothesis 2.1A** – Average supine SBP will be significantly increased following droxidopa administration compared to placebo.
 - This hypothesis will be tested using a repeated measures analysis of covariance where the pre-droxidopa or placebo SBP will be used as the covariate and the adjusted post-test scores will serve as the dependent variable. In addition, the covariate adjusted point estimate and 95% confidence interval of the difference between drug conditions will provide the first reported estimate of the supine SBP response to droxidopa versus placebo in the SCI population.
- **Hypothesis 2.1B** – The proportion of supine BP observations $\geq 140/100$ mmHg following droxidopa administration will not differ significantly from the proportion observed during the placebo trial.
 - This hypothesis will be tested by performing separate (one each for systolic and diastolic pressure) tests of the differences between dependent proportions, from which the 95% confidence intervals will be calculated. The presence of zero in a confidence interval will indicate a lack of statistical difference in incidence of hypertensive events between the droxidopa and placebo conditions.
- **Hypothesis 2.2** – Average SBP during 70° HUT will be significantly increased following droxidopa administration compared to placebo.
 - This hypothesis will be tested by performing a dependent t-test between the mean SBP during 70° HUT comparing droxidopa to placebo. Further, the point estimate and resulting 95% confidence interval will provide an estimate of the SBP response to HUT of droxidopa versus placebo in the SCI population.
- **Hypothesis 2.3** – The change in CBFv from supine to HUT will be significantly attenuated following droxidopa administration compared to placebo.

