d. Justify any exclusion of specific gender, age, and racial or ethnic groups:

N/A

6. State inclusion criteria for enrollment in study:

Study 1:

- 1) Male or Female, age 18 to 89 with traumatic SCI.
- 2) SCI Subjects (n=40):
 - a) Any level of injury;
 - b) Any AIS grade of SCI;

- c) Non-ventilator dependent
- d) Primarily wheelchair dependent for mobility;
- e) Duration of injury < 1 year

3) Low Blood Pressure:

Systolic BP less than 110 mmHg and/or diastolic BP less than 70 mmHg for males;
Systolic BP less than 100 mmHg and/or diastolic BP less than 70 mmHg for females;

4) Primary Language is English.

Able to provide informed consent

Study 2:

5) Male or Female, age 18 to 89 with traumatic SCI.

6) SCI Subjects (n=40):

- a) Any level of injury;
- b) Any AIS grade of SCI;
- c) Non-ventilator dependent
- d) Primarily wheelchair dependent for mobility;
- e) Duration of injury < 1 year

7) Low Blood Pressure:

Systolic BP less than 110 mmHg and/or diastolic BP less than 70 mmHg for males;
Systolic BP less than 100 mmHg and/or diastolic BP less than 70 mmHg for females;

8) Primary Language is English.

Able to provide informed consent

9) Showed a normotensive blood pressure in response to Droxidopa during study 1.

7. State exclusion criteria for enrollment in study:

Study 1 and Study 2:

- Current illness or infection
- Individuals with frequent or severe autonomic dysreflexia
 - a. More than 3 symptomatic events per week
 - b. BP \geq 140/90 mmHg
 - c. Significant adverse subjective symptoms reporting
- Hypertension
- Any neurological condition other than SCI (Alzheimer's disease, dementia, stroke, multiple sclerosis, Parkinson's disease, etc.)
- History of epilepsy or other seizure disorder
- History of traumatic brain injury (TBI)
- Liver or kidney disease
- Bladder problems including blockage of the urine and/or weak urine stream.
- Diagnosis of a psychiatric disorder such as schizophrenia or bipolar disorder
- Known artery disease, heart failure, AV block, and irregular heartbeat
- Any allergies to droxidopa, aspirin, polyethylene oxide, polyethylene glycol, hydroxypropyl cellulose, butylated hydroxytoluene, magnesium stearate, hypromellose, yellow ferric oxide, and red ferric oxide
- Major surgery in the last 30 days
- Illicit drug abuse in the past 6 months
- Pregnant
- Your prescription medications will be reviewed by the study investigators and research staff.

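### Safety #2 covers supine BP, but diastolic pressure is analysed only as readings at or above 100 mmHg; no mean supine diastolic effect is estimated, and a null threshold result would be weak evidence of no effect.

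*Protocol*

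**What the plan says.** Both documents list supine BP as Safety #2 and give the same two analyses (Protocol, Data Analysis, Secondary Aims; Combined protocol and SAP, item 17a).

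- **Hypothesis 2.1A** is continuous and systolic only: "Average supine SBP will be significantly increased following droxidopa administration compared to placebo". It uses a repeated-measures analysis of covariance with the pre-dose value as covariate, and it promises an adjusted difference with a 95% CI.
- **Hypothesis 2.1B** concerns "The proportion of supine BP observations $\geq 140/100$ mmHg" and predicts no difference between conditions. It is tested by "separate (one each for systolic and diastolic pressure) tests of the differences between dependent proportions". The reading rule is "The presence of zero in a confidence interval will indicate a lack of statistical difference". No margin is stated.

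Neither document plans an analysis of mean supine diastolic pressure. The Protocol (Study 2) has supine brachial BP recorded at 0, 10, 20, 30, 40, 50 and 60 minutes, after a baseline supine period, so the values will exist.

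On who enters, the Protocol (Screening Visit) requires low seated systolic pressure or orthostatic hypotension, and that "there is no evidence of sustained elevation in BP \geq 140/100 mmHg in either the supine or seated positions". The Combined document (item 6) has "Systolic BP less than 110 mmHg and/or diastolic BP less than 70 mmHg for males", with a lower systolic limit for females. Study 2 takes only those whose seated systolic pressure became normal in Study 1.

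**The concern.** Many participants are selected for low pressure, so a diastolic cut at 100 mmHg may lie well above most of their supine readings. Someone at 70 mmHg must rise by 30 mmHg to count. After a 10 mmHg rise, only a reading that would otherwise have been 90 mmHg or more counts.

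The direction of the hypothesis makes this matter. 2.1B predicts no difference and takes an interval containing zero as its answer, so an endpoint that seldom occurs tends to favour the predicted result. A diastolic pressor effect could be present and the safety conclusion still read as no difference.

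The pilot is also meant to inform a larger trial on utility and safety. It will supply a supine systolic effect in mmHg with a CI, but no diastolic counterpart.

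A related point is that the Safety Monitoring section acts on BP sustained above 140/90 mmHg, while 2.1B counts from 140/100 mmHg. A diastolic pressure of 90 to 99 mmHg can therefore prompt action in the laboratory and not appear in the diastolic analysis.

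**Working it through.** The plan states no power, event rate or effect size for 2.1B, so there is no figure to reproduce.

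**Inputs from the documents.** Study 2 size is 25 (Protocol: "We anticipate that 25 subjects will respond to droxidopa with a normal seated SBP") or 30 (Combined document, item 4). Each participant receives both conditions. There are 7 supine readings per visit, 6 of them after minute 0. The diastolic threshold is 100 mmHg.

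**Assumptions, because no supine diastolic distribution is given.** Normal readings; placebo mean 60 to 80 mmHg; total SD 10, with variance split 60% between persons, 20% visit and 20% reading; a uniform rise of 10 mmHg unless stated.

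**Event rates.** P(reading ≥100) = 1 − Φ((100 − mean)/SD). At mean 70 this is 1 − Φ(3.0) = 0.1% on placebo and 1 − Φ(2.0) = 2.3% after the rise. With 25 × 6 = 150 droxidopa readings, 150 × 0.0228 = 3.4 are expected to count.

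**Simulated crossover (4,000 runs per case).** Power is shown for n = 25 / n = 30, using two participant-level methods: a paired CI on each person's share of readings ≥100, and a paired Wald CI on having any reading ≥100.

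| Placebo mean | P(≥100), placebo → droxidopa | Expected droxidopa events (n = 25) | No event in either condition (n = 25) | Power, share | Power, any reading |
|---|---|---|---|---|---|
| 60 | 0.003% → 0.1% | 0.2 | 88% | 0 / 0% | 0 / 0% |
| 65 | 0.02% → 0.6% | 0.9 | 59% | 0.1 / 0.1% | 0.2 / 0.2% |
| 70 | 0.1% → 2.3% | 3.4 | 18% | 2 / 3% | 6 / 10% |
| 75 | 0.6% → 6.7% | 10 | 1% | 27 / 38% | 47 / 59% |
| 80 | 2.3% → 15.9% | 24 | 0% | 80 / 90% | 86 / 93% |

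**Dependence on the method.** The plan does not say which paired-proportion method or unit is meant. At n = 25, if all discordant pairs point one way, at least 4 are needed to exclude zero with a Wald CI and 6 with exact McNemar (2 × 0.5⁶ = 0.031, whereas 2 × 0.5⁵ = 0.063). With SD components 8/5/5 (total √114 = 10.7), mean 70 and a 10 mmHg rise, power for n = 25 / 30 is 1.0 / 2.7% by exact McNemar on any reading and 13.5 / 19.8% by Wald CI. A Wald CI on pooled readings gives 49 / 56%, but it ignores the clustering of readings within persons and is anticonservative.

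**Dependence on the response.** If individual rises vary with SD 12 mmHg around the mean of 10 (total SD 10, n = 25), power by share / any reading becomes 8 / 24% at mean 65, 38 / 61% at mean 70 and 94 / 92% at mean 80.

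**Comparator: paired test of mean supine diastolic pressure**, a simple stand-in for the 2.1A model. With total SD 10 (variance 100), the variance of the paired difference is 2 × (20 + 20/6) = 46.7 under a uniform response, an SD of 6.8. Adding response SD 12 gives √(46.7 + 144) = 13.8. Simulated power was 91% or more in every scenario. In general the noncentrality is 10 ÷ (SD/√n):

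| SD of paired difference | Power, n = 25 | Power, n = 30 |
|---|---|---|
| 10 | 99.8% | over 99.9% |
| 12 | 97.9% | 99.3% |
| 15 | 89% | 94% |
| 20 | 67% | 75% |

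**The case against.** A reader might infer that the diastolic test can hardly register an event, or that it will report no difference whatever droxidopa does to diastolic pressure. The documents do not support that.

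- Entry is not confined to low diastolic pressure. The Protocol admits participants on orthostatic hypotension alone, its definition of hypotension is systolic, and its low-pressure criterion is measured seated while the endpoint is supine. The diastolic limit of 70 mmHg appears only in the Combined document, joined by and/or. Only sustained elevation is excluded.
- No supine diastolic mean or SD is given. At a mean of 80 mmHg the threshold test works well.
- Responses vary. The preliminary droxidopa data show systolic changes of 9.0 ± 10 and 18.6 ± 16 mmHg in two subgroups, and variable responses raise the event count.

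The defence can add that 2.1B asks about hypertensive events, not mean shifts, and raising pressure is the aim of the drug. The plan also says that "the following statistical analyses are not powered for a specific effect size". Diastolic pressure is further watched through the action rule, the clinician's review of recordings and the independent monitor.

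All of this limits how large the problem is. Three things remain. Pilot status explains the absence of powering, but not the reading of an interval containing zero as no difference. Monitoring is not a planned effect estimate. And Safety #2 names supine BP as a whole, yet only its systolic part is estimated in mmHg.

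**Conclusion.** The design point stands on the text alone: supine diastolic pressure is analysed only through the 100 mmHg cut, and no mean effect is estimated.

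Its consequence is conditional. For a uniform 10 mmHg rise and 25 to 30 participants, participant-level threshold tests have roughly 0-20% power if supine diastolic pressure averages about 70 mmHg or less with SD about 10-11. Under the tabulated assumptions this becomes 27-59% at a mean of 75 and 80-93% at a mean of 80, and variable responses raise it further. A paired analysis of the mean is about 90% or better in the simulated scenarios, falling to 67-75% if the SD of the paired difference is 20 mmHg. Every one of these figures rests on assumed distributions.

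A null diastolic result under 2.1B should therefore not be read as showing no supine diastolic effect. Whatever its power, that test gives the next trial no diastolic estimate in mmHg. This is an improvement that should be made, not a flaw that invalidates the trial.

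**What to change.** 1. Add supine diastolic pressure to Hypothesis 2.1A: the same baseline-adjusted repeated-measures model, with pre-dose supine diastolic pressure as covariate. Report the droxidopa-placebo difference with its 95% CI as the diastolic effect estimate for Safety #2.
2. Keep the 100 mmHg result in 2.1B as counts of participants and of readings by condition, with its CI. Remove the rule that zero inside the interval indicates no difference.
3. Reconcile the 140/90 action level under Safety Monitoring with the 140/100 analysis threshold, or explain why they differ.

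The cost is a change of wording in both documents and one more model on readings already planned, with no new measurement. The downside is one additional secondary estimate.

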Following identification of the optimal dose subjects will undergo a washout period of no less than 2 and no more than 10 days. The minimum 2-day washout was chosen because of the known 2- to 3-hour plasma half-life of droxidopa. [17]

Study 2 – To determine the effect of droxidopa, compared to placebo, on: 2.1A) supine SBP (mmHg); 2.1B) proportion of supine BP observations \geq 140/100 mmHg; 2.2) SBP during a HUT and 2.3) change in CBFv from supine to HUT. Within about 1 week of determining the dose of droxidopa that normalizes seated SBP eligible participants will return to the laboratory for the placebo-controlled randomization trial. Subjects will arrive at the laboratory between 10AM and 1PM after a light breakfast and having avoided alcohol, caffeine, and nicotine for 12-hours. Subjects will remain in their wheelchair for instrumentation, which will include: 1) ECG, 2) brachial BP, 3) finger arteriolar BP and 4) CBFv. After instrumentation subjects will be transferred to the supine position (on the tilt table) for a 10-minute period of quiet rest and baseline supine data collection. Participants will then be administered either oral droxidopa or matching placebo in a double-blinded manner and will remain in the supine

position for 60 minutes. Supine HR, finger BP and CBFv will be monitored continuously for 5-minutes at 0, 25 and 55 minutes, supine brachial BP will be monitored and recorded at 0, 10, 20, 30, 40, 50 and 60 minutes. The HUT maneuver will be initiated 60 minutes post-droxidopa/placebo

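### The tilt-SBP comparison (Hypothesis 2.2) uses neither the pre-dose baseline nor a period term; precision may be lost, and unequal sequences would let part of any period effect into the estimate

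*Protocol*

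**What the plan says.** Protocol, Data Analysis, Hypothesis 2.2, and the same hypothesis in item 17a of the combined protocol and SAP, plan the test as "performing a dependent t-test between the mean SBP during 70° HUT comparing droxidopa to placebo". The point estimate and 95% CI are to be reported. No covariate, period or sequence term is named.

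The rest of the plan bears on this in four ways:

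- **Design.** Under Study Population in the Protocol, each Study 2 participant is randomised "to receive either droxidopa/placebo or placebo/droxidopa". No blocking or sequence ratio is stated.
- **Baseline.** At the Study 2 visits the participant lies supine "for a 10-minute period of quiet rest and baseline supine data collection". Only after that: "Participants will then be administered either oral droxidopa or matching placebo in a double-blinded manner". Tilt starts 60 minutes after dosing.
- **Other hypotheses.** For Hypothesis 2.1A (supine SBP), "the pre-droxidopa or placebo SBP will be used as the covariate". Hypotheses 2.3 and 2.4 use ANCOVA with pre-tilt values as covariates. No reason is given for leaving 2.2 unadjusted, and none of these analyses names a period term.
- **Size and purpose.** The Protocol says "We anticipate that 25 subjects will respond to droxidopa with a normal seated SBP"; item 4 of the combined document gives 30 for Study 2. The trial is a pilot without a powered effect size, and its results are to be used to power a larger trial.

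**The concern.** The pairing removes stable differences between people. What remains in the error is how a person differs from one visit to the other. A pre-dose reading taken the same day may explain some of that, and the visit's own treatment cannot have changed it. Hypothesis 2.2 leaves the reading unused although it has been recorded.

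The plan also does not separate treatment from visit order. If tilt SBP shifts between the first and second visit for any reason, the shift adds to the spread of the paired differences. With unequal sequences, part of it also moves the mean difference.

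At stake are the width and centring of the interval for Efficacy #2. A paired SD that contains removable variation could also feed into the size of the next trial.

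**Working it through.** **No figure to reproduce.** The documents state no power, SD or CI width for Hypothesis 2.2.

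**Inputs**

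- n = 25 (Protocol, Study Population) and n = 30 (combined document, item 4).
- Two-sided 5%, inferred from the 95% CI.
- SD of the paired difference, SDd: not given. The Protocol's section on anti-hypotensive treatment in SCI gives between-subject SDs of orthostatic SBP of 24 and 26 mmHg under two other drugs. Taking 25 and an assumed within-person correlation r, SDd = 25 × √(2(1 − r)). This is 25 at r = 0.5, 20 at r = 0.68 and 16 at r = 0.8.
- rho, the correlation between the drug-minus-placebo difference in pre-dose supine SBP and that in tilt SBP: not given; 0 to 0.7 assumed.

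**Step 1: planned interval.** Half-width = t(0.975, n−1) × SDd / √n. For SDd = 20:

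- n = 25: 2.064 × 20/5 = 8.26 mmHg
- n = 30: 2.045 × 20/5.477 = 7.47 mmHg

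For SDd of 16 and 25 the half-widths are 6.6 and 10.3 (n = 25), and 6.0 and 9.3 (n = 30).

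**Step 2: interval with baseline and period.** Regressing the paired difference on sequence and on the baseline difference leaves n − 3 degrees of freedom. With balanced sequences and no period effect, the ratio to the planned half-width is

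√[(1 − rho²)(1 + 1/(n−4))] × t(n−3)/t(n−1).

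At rho = 0 and n = 25 this is √(1 + 1/21) × 2.074/2.064 = 1.03. The equivalent gain in participants is 1/ratio² − 1, from unrounded ratios.

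| rho | Ratio, n=25 | Half-width, SDd 20 | Ratio, n=30 | Half-width, SDd 20 | Equivalent participants |
|---|---|---|---|---|---|
| 0 | 1.03 | 8.49 | 1.02 | 7.63 | about 4-5% fewer |
| 0.3 | 0.98 | 8.10 | 0.98 | 7.28 | about 4-5% more |
| 0.5 | 0.89 | 7.35 | 0.89 | 6.61 | about 26-28% more |
| 0.7 | 0.73 | 6.06 | 0.73 | 5.45 | about 85-88% more |

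Setting the ratio to 1 gives break-even at |rho| = 0.23 (n = 25) and 0.21 (n = 30). In simulation (4,000 runs per setting), simple randomisation with rho = 0 and no period effect gave ratios of 1.05 (n = 25) and 1.04 (n = 30). The worst case is thus about 2-5% wider.

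In power terms, for an assumed 10 mmHg effect with SDd 20 and n = 25, the plan has 67%. The adjusted analysis has 65%, 69%, 77% and 90% at rho = 0, 0.3, 0.5 and 0.7.

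**Step 3: period effect in the error.** In an AB/BA design, a first-to-second-visit effect p shifts each drug-minus-placebo difference by +p or −p according to sequence. With balanced sequences the SD becomes √(SDd² + p²). For p = 5 mmHg:

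- SDd 16: √281/16 = 1.05
- SDd 20: √425/20 = 1.03
- SDd 25: √650/25 = 1.02

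A much larger period effect, half of SDd, gives √(1 + 0.25) = 1.12. In simulation with balanced sequences the paired t-test then had a type I error of about 2.5-3%, so it is conservative.

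**Step 4: period effect in the estimate.** With sequence sizes n1 and n2 the paired mean shifts by p × (n1 − n2)/n.

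- 13/12: 1/25 = 4% of p
- 15/10: 5/25 = 20% of p
- 18/12: 6/30 = 20% of p

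If randomisation were simple, a split of 15/10 or worse would have probability 42% at n = 25, and 18/12 or worse 36% at n = 30 (binomial tails).

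**The case against.** The strongest reply is that the planned test is valid. Pairing has already removed stable between-person variation, and with balanced sequences a period effect makes the test conservative rather than wrong. Neither rho nor a period effect is documented. If both are absent, the adjusted analysis gives a slightly wider interval. All of this stands.

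Three more specific replies also stand:

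- Hypothesis 2.1A adjusts a supine outcome for a supine baseline. Tilt SBP is measured in another posture, 60 to 90 minutes after dosing, so a useful rho cannot be taken for granted.
- Hypothesis 2.2 is a secondary aim of a pilot. The plan says that its results in general will power a later trial, without naming this estimate.
- The missing period term is common to the Study 2 analyses, so it is not a fault of Hypothesis 2.2 alone.

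A reader might also infer from the Protocol's background that large day-to-day swings make a gain certain. The text speaks of wide, frequent fluctuations and circadian dysregulation. It does not quantify variation between days, and rapid within-day fluctuation could weaken the link between a pre-dose reading and later tilt SBP.

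These replies leave the balance of cost and benefit in place: a small bounded loss against a possibly large gain, from data already recorded.

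**Conclusion.** The point holds as a conditional one about efficiency and robustness. Precision may be lost under the planned test. The adjusted analysis narrows the interval if |rho| exceeds about 0.2 or there is a sufficient period effect: by about 2%, 11% and 27% at rho = 0.3, 0.5 and 0.7. Otherwise it costs at most about 2-5% of width. The conclusion is the same at n = 25 and n = 30. A 5 mmHg period effect adds only about 5% to 2% to the paired SD for SDd of 16 to 25. The period term matters more for bias: at a 15/10 split, 20% of any period effect sits in the planned estimate.

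rho, SDd, the period effect and the 10 mmHg effect used for power are all assumptions. A reader might infer that precision is certainly being lost, or that the t-test is invalid. The documents support neither reading: they give no correlation and no period effect, and they do not state the sequence ratio.

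**What to change.** Prespecify for Hypothesis 2.2 a linear regression of each participant's drug-minus-placebo difference in mean tilt SBP on:

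1. sequence, coded +1/−1, which is the period adjustment; and
2. the within-person drug-minus-placebo difference in **pre-dose** supine SBP, left uncentred.

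The intercept is then the treatment effect at zero baseline difference. Report it with its 95% CI, and keep the paired t-test as a sensitivity analysis.

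Two details matter. The covariate must not be the supine value at 60 minutes, just before tilt, because treatment may already have changed it. It should also be the within-person difference: a raw visit-level baseline in a random-participant model mixes between-person and within-person slopes. State which pre-dose readings make up the baseline.

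Add the period term to the other continuous Study 2 comparisons (Hypotheses 2.1A, 2.3 and 2.4) as well.

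The cost for Hypothesis 2.2 is a change of wording in both documents, two further degrees of freedom out of 24 to 29, and a CI about 2-5% wider if there is neither a baseline correlation nor a period effect. No new data are needed.
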